5.6. Lifestyle and Diet

Subjects should be advised that driving ability, operation of machinery and work without a secure fit may be affected by adverse reactions such as dizziness and visual disturbances.

There are no trial restrictions with respect to smoking. Moderate consumption of caffeine (tea, coffee, cola, energy drinks etc.) and alcoholic beverages (such as 200 mL of beer or 100 mL wine per day) will be permitted. Grapefruit consumption and quinine-containing drinks should be avoided.

Additional information regarding contraindications, precautions and warnings concerning IMP are provided in the current version of the IB. [31]

5.7. Further Treatment after the End of the Trial

After the end of the trial, the subjects will be treated according to local standard practice.

6. ASSESSMENTS

The schedule of tests performed is described in the trial flow chart (Page 12).

All measurements performed in this trial are recognised standard methods. Therefore, no further details concerning reliability or relevance will be discussed here.

6.1. Description of Trial Visits

Seven on-site visits and five phone call visits are planned.

Due to the PVT and MoCA assessments on-site visits should always start in the morning.

Unscheduled (on-site or phone) visits at additional time points may be performed, if required. An administrative/logistic phone contact or on-site presence will not be documented as unscheduled visit in the eCRF.

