## 2. OBJECTIVES AND DESIGN

### 2.1 Trial Objectives

#### 2.1.1 Primary Objective

The primary objective of this trial is to assess the safety profile of THN102 (modafinil/flecainide combination) at two doses (200 mg/18 mg and 200 mg/2 mg) versus placebo in subjects with excessive daytime sleepiness associated with Parkinson's disease (PD).

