**Table 5: Visit Numbering and Labels**

Visit number	Visit name	Label in Statistical Output
10	Screening – VS1	VS1
20	Actigraphy – VS2	VS2
30	Baseline – VR	VR
40	Actigraphy – V1A	V1A
50	End of treatment I – V1B	V1B
60	End of washout I – V1C	V1C
70	Actigraphy – V2A	V2A
80	End of treatment II – V2B	V2B
90	End of washout II – V2C	V2C
100	Actigraphy – V3A	V3A
110	End of treatment III – V3B	V3B
120	Early Discontinuation Visit – EDV	EDV
130	Follow-up – V3C	V3C

The values collected at the EDV will be slotted according to date of EDV occurrence (see Section 4.6).

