### Endpoint value

The endpoint value for a variable is defined as the last non-missing value collected during any end-of-treatment visit (V1B, V2B, or V3B).

For diary data, the endpoint value will be the value standardized as described in Section 5.6.8 over any treatment period corresponding to a given treatment.

**Absolute change from baseline** will be calculated as

$$\text{Absolute Change from Baseline at Visit } X = \text{Value at Visit } X - \text{Baseline Value}$$

**Relative change from baseline (%)** will be calculated as

$$\text{Relative Change from Baseline at Visit } X = \frac{\text{Value at Visit } X - \text{Baseline Value}}{\text{Baseline Value}} \times 100$$

Note: Subjects with a baseline value of '0' will be excluded from the calculation of relative change.

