## 4.8 Treatment Assignment

In summaries and analyses where data is pooled by treatment, assignment to treatments will be performed as follows:

- Data collected up to and including visit VR (baseline) will be assigned to all treatments.
- Data collected at visits V1A-V1C, V2A-V2C, V3A-V3B, will be assigned to the treatment corresponding to the first, second and third treatment period respectively
- Data collected at the EDV visit will be assigned to treatment periods according to the rules in Section 4.6
- Efficacy analyses will be performed according to treatment **as randomised**. Data will be assigned to treatments based on the combination of planned treatment sequence and treatment period.
- Safety analyses will be performed according to treatment **as treated**. Data will be assigned to treatments based on the treatment actually received during the corresponding treatment period.

Other features of or deviations from the rules of treatment assignment are discussed in the relevant sub-sections of Section 5.

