## 5.5.2 Clinical Laboratory Evaluation

Clinical laboratory values (haematology, biochemistry, and urinalysis) are collected at visit VS1, VR, V1B, V2B, and V3B/EDV for each laboratory parameter.

The following parameters are collected:

**Haematology:** Leukocytes, erythrocytes, haemoglobin, haematocrit, MCV, MCH, platelets, neutrophils, lymphocytes, monocytes, eosinophils, basophils, neutrophils (%), lymphocytes (%), monocytes (%), eosinophils (%), basophils (%).

**Biochemistry:** sodium, potassium, urea, creatinine, total protein, albumin, total bilirubin, direct bilirubin, AST (GOT), ALT (GPT), alkaline phosphatase, uric acid, glucose (fasting and non-fasting), cholesterol, triglycerides.

**Urinalysis:** Leukocytes, nitrites, pH, protein, glucose, ketones, urobilinogen, bilirubin, blood, haemoglobin.

Haematology and biochemistry test results are assigned an LNH classification according to whether the value is lower than (L), within (N) or higher than (H) the reference range for that parameter as provided by the corresponding laboratory.

Clinical significance of laboratory values is evaluated by the investigator.

Range values of laboratory results will be set to ½ of the specified threshold for analysis (e.g. a result of “<0.03” will be considered as 0.015 in summaries).

The following tables and listings will be provided:

Table 15.2.4.1.1.T Summary of Clinical Laboratory Tests: Haematology – Safety

Table 15.2.4.1.2.T Summary of Clinical Laboratory Tests: Biochemistry – Safety

Table 15.2.4.1.3.T Summary of Clinical Laboratory Tests: Urinalysis – Safety

The default summary statistics of clinical laboratory test results will be presented at each visit. The absolute change from baseline will be presented for haematology and biochemistry findings.

Table 15.2.4.2.1.T Clinical Laboratory Tests: Incidence of Haematology Abnormalities – Safety

Table 15.2.4.2.2.T Clinical Laboratory Tests: Incidence of Biochemistry Abnormalities – Safety

Number and percentage of subjects for each laboratory parameter will be displayed in CS Low, Low, Normal, High, and CS High categories. Percentage will be based on the number of subjects at specified visit.

Table 15.2.4.2.3.T Clinical Laboratory Tests: Incidence of Urinalysis Abnormalities – Safety

Number and percentage of subjects with abnormal values of urinalysis parameters will be displayed in normal/abnormal/CS abnormal categories. Percentage will be based on the number of subjects at specified visit.

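### The SAP has no by-treatment row for laboratory, ECG and vital-sign values from unscheduled visits or unslotted early discontinuation visits, so out-of-range values not reported as adverse events appear only in listings

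*Protocol*

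**What the plan says.** **Unscheduled visits exist and are recorded.** Protocol 6.1: "Unscheduled (on-site or phone) visits at additional time points may be performed, if required". The next sentence, "An administrative/logistic phone contact or on-site presence will not be documented as unscheduled visit in the eCRF", implies that the other unscheduled visits are documented there. Protocol 7.1.4 says that adverse event (AE) data are gathered at them.

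**The SAP works by named visit.** SAP Table 5 has 13 labels: the 12 scheduled visits and EDV. For data after baseline, SAP 4.8 says: "Data collected at visits V1A-V1C, V2A-V2C, V3A-V3B, will be assigned to the treatment corresponding to the first, second and third treatment period respectively". EDV data are sent to the rules in SAP 4.6.

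**Tables.** In SAP 5.5.2 the abnormality tables carry the rule "Percentage will be based on the number of subjects at specified visit", and SAP 5.5.3 and 5.5.4 repeat it for vital signs and ECG. The laboratory and vital-sign shift tables run from baseline to endpoint, and SAP 4.7 states: "The endpoint value for a variable is defined as the last non-missing value collected during any end-of-treatment visit (V1B, V2B, or V3B".

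**Objective.** "The primary objective of this trial is to assess the safety profile of THN102", at two doses against placebo (SAP 2.1.1).

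**The concern.** Safety is the primary objective, yet on-drug measurement is sparse: one laboratory sample, one ECG and one set of supine and standing vital signs per treatment period, at its end. The mid-period contacts V1A, V2A and V3A are phone calls. An earlier on-drug value can come only from an unscheduled visit or an EDV, and these are the two sources for which the table rules are missing or incomplete.

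The need for such measurements is foreseeable. Protocol 4.4.2 lists liver-enzyme and ECG findings among the reasons for withdrawal, SAP 5.5.1 records whether an AE required tests, and Protocol 1.4.1 reports a small but significant rise in blood pressure and heart rate in trial THN102-101. At stake is whether the by-treatment abnormality tables show every on-treatment value collected or only those from the end-of-period visit.

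**Working it through.** The plan gives no figure on this point to reproduce. The check sets the rules side by side.

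**1. On-drug assessments per period.** From the flow chart:
- Laboratory: VS1, VR, V1B, V2B, V3B (5 visits).
- ECG and vital signs: the same plus V1C and V2C (7 visits); those two are end-of-washout visits.
- On drug: V1B, V2B and V3B only, so 3 visits / 3 periods = 1 per period. V1B is at Day 14 ±2, that is Days 12 to 16.

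**2. An unscheduled laboratory, ECG or vital-sign value within a treatment period.**

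| Output | Rule | Result |
|---|---|---|
| Laboratory and vital-sign shift tables (15.2.4.3.x.T, 15.2.5.3.T) | Endpoint from V1B, V2B or V3B (SAP 4.7) | Excluded by definition |
| Abnormality tables (15.2.4.2.x.T, 15.2.5.2.T, 15.2.6.3.T) | Percentage of subjects at the specified visit | No row described |
| ECG shift table (15.2.6.4.T) | Percentage of subjects at the specified visit; endpoint not mentioned | No row described |
| Treatment-emergent AE (TEAE) tables | Onset date (SAP 5.5.1) | Included if reported as an AE |
| Listings | Values listed | Shown |

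Values taken before VR are not affected: SAP 4.8 assigns them to all treatments and SAP 4.7 lets them serve as baseline.

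**3. EDV values.** SAP 4.6 slots an EDV to the end of treatment if there were at least 7 intakes and the last was no more than 3 days earlier. It slots an EDV to the end of washout if the last intake was 6 or more days earlier. This leaves no slot for:
- an EDV during treatment after fewer than 7 intakes;
- an EDV more than 3 but fewer than 6 days after the last intake.

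SAP 5.6 classes every EDV by the preceding scheduled visit, but only for its own efficacy rules.

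**4. What the AE route recovers.** Protocol 6.3.2 makes a change to a clinically significant laboratory value an AE, with stated exceptions. ECG and vital signs have no matching sentence and rely on the general definition in Protocol 7.1.1. The planned tables count more than this: Low and High laboratory values not judged significant, and any blood pressure or heart rate outside SAP Table 6. Such values need not become AEs.

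**5. Scale.** With the planned 60 subjects per treatment, k subjects whose only abnormal value falls outside the tabulated visits lower that treatment's incidence by 100 × k/60 percentage points:
- k = 1: 1.7
- k = 3: 5.0
- k = 5: 8.3

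The values of k are assumptions; the documents give no rate of unscheduled visits.

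**The case against.** The strongest reply is that adverse events are the first-listed safety endpoint and do not depend on visit labels. They are collected at unscheduled visits, assigned to treatment by onset date, and tabulated by treatment, seriousness, relationship and severity. This stands. A reader might infer that unscheduled findings are left out of the primary safety comparison; the documents do not support that, because clinically significant findings should reach the TEAE tables.

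Nor is it right that these values have no treatment. SAP 4.6 defines periods by date, and SAP 4.8 adds for safety data: "Data will be assigned to treatments based on the treatment actually received during the corresponding treatment period". A treatment can be derived. What is missing is an instruction to do so and a table row to receive the value.

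Three further limits stand:
- Absence from the by-visit tables is read from the SAP's silence, and the table shells attached to it were not available. Exclusion from the laboratory and vital-sign shift tables is explicit.
- Protocol 6.1 does not say why an unscheduled visit takes place or which tests are done, and phone visits yield no measurements. That the values are prompted by suspected harm is plausible but not stated.
- A reader might infer a bias against placebo of a definite size. With no visit rate and no split by treatment in the documents, neither size nor direction can be shown.

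Finally, common scheduled visits keep ascertainment equal across treatments, whereas a worst-value row does not. This is a fair reason to keep the by-visit rows as they are and to disclose the number of extra assessments. It is not a reason to leave collected values untabulated.

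**Conclusion.** The point holds as a gap in the safety tabulation that is cheap to close. On-treatment unscheduled values are excluded from the laboratory and vital-sign shift tables by the endpoint definition, and the SAP text gives them no row in the laboratory, vital-sign or ECG abnormality tables. Some EDV values have no slot at all, which affects subjects who stop early. The loss is mainly of out-of-range values not recorded as AEs. Its size is unknown; 1.7 percentage points per affected subject is a unit of scale that assumes 60 subjects per treatment, not an estimate. The conclusion rests on the SAP text without its table shells, and on the AE reporting rules being followed.

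**What to change.** For safety data only:

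1. **SAP Table 5 and 4.8.** Add an unscheduled label. Assign unscheduled assessments, and EDV assessments that SAP 4.6 leaves unslotted, by date to the SAP 4.6 treatment period in which they fall, or to the preceding treatment if they fall in washout. SAP 5.5.1 already does this for AE onset. State that a period cut short closes at the EDV, since SAP 4.6 ends treatment periods only at V1B, V2B or V3B.
2. **Abnormality tables 15.2.4.2.1.T to 15.2.4.2.3.T, 15.2.5.2.T and 15.2.6.3.T.** Add one row: *any time on treatment (worst value, scheduled, unscheduled or EDV)*, with subjects treated in that period as denominator. Where a parameter can be low or high, count each direction.
3. **Shift tables 15.2.4.3.1.T to 15.2.4.3.3.T, 15.2.5.3.T and 15.2.6.4.T.** Add a shift from baseline to worst on-treatment value, with the same denominator.
4. **Footnote** the number of unscheduled assessments per treatment, because ascertainment may differ between treatments, and say how washout values are handled.

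Leave the by-visit rows, the existing baseline-to-endpoint shifts and the efficacy analyses unchanged. The cost is a few lines of SAP text and one addition to each of ten tables, using data already collected. The rule should be fixed before unblinding; chosen later, it would be a post hoc decision on the primary objective.

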6.1.1. Visit VS1

This screening visit 1 is an on-site visit and will take place between Day -15 and Day -7.

The following procedures will be performed:

- Informed consent
- Hand out subject card
- Demography (incl. height measurement)
- Medical history, prior medication
- Concomitant medication
- Hoehn & Yahr staging
- Check for eligibility
- Adverse event collection
- Safety laboratory (blood [including serology and blood coagulation], urine)
- Pregnancy test (urine), for women of childbearing potential only
- Vital signs (after 5 minutes of supine rest and after 2 minutes in standing position, i.e. 1 set)
- Weight
- 12-lead ECG (10 min supine)
- C-SSRS Screening version
- Physical examination
- ESS
- MoCA
- Issue actigraphy device (fully charged)
- Issue subject diary (screening phase diary)

6.1.2. Visit VS2

This screening visit 2 is a phone call visit and will take place on Day -5 ±1.

The following procedures will be performed:

- Concomitant medication
- Check for eligibility
- Adverse event collection
- Remind subject to wear actigraphy device

6.1.3. Visit VR

This randomisation/baseline visit is an on-site visit and will per definition take place on Day -1.

(Please note that there is no Day 0. The day after Day -1 is Day 1. Day 1 is the day of first IMP intake.)

The following procedures will be performed:

- Concomitant medication
- Check for eligibility
- Randomisation
- IMP dispensation
- Adverse event collection
- Safety laboratory (blood, urine)
- Pregnancy test (urine), for women of childbearing potential only
- Vital signs (3 sets of orthostatic vital signs 15-20 min apart)
- Weight
- 12-lead ECG (10 min supine)
- C-SSRS Since Last Visit version
- MDS-UPDRS
- QUIP-RS
- Physical examination
- ESS
- PVT at 10:00 h, 12:00 h, 14:00 h and 16:00 h (\pm 0:15 h each). If this PVT assessment schedule is too burdensome for the subject, it may be individually adapted to at least 3 assessments, with a time window of not less than 1 h between two PVT assessments. Once chosen, the timeframe should remain constant during the trial for each subject. Upload data
- MoCA
- Collect and charge actigraphy device
- Read out actigraphy device, upload data
- Issue actigraphy device (fully charged)
- Issue subject diary (treatment phase diary)
- Check subject diary (screening phase diary)
- Collect subject diary (screening phase diary)
- PK blood sample

6.1.4. Visits V1A, V2A and V3A

These actigraphy sensor visits are phone call visits and will take place

- on Day 10 \pm 1 (V1A)
- on Day 31 \pm 1 (V2A)
- on Day 52 \pm 1 (V3A)

The following procedures will be performed:

- Concomitant medication
- Adverse event collection
- Remind subject to wear actigraphy device

6.1.5. Visits V1B, V2B and V3B

These end-of-treatment period visits are on-site visits and will take place

- on Day 14 \pm 2 (V1B)
- on Day 35 \pm 2 (V2B)
- on Day 56 \pm 2 (V3B)

The following procedures will be performed:

- Concomitant medication
- IMP accountability, compliance check, collect IMP
- Adverse event collection
- Safety laboratory (blood, urine)
- Pregnancy test (urine), for women of childbearing potential only
- Vital signs (after 5 minutes of supine rest and after 2 minutes in standing position, i.e. 1 set)
- Weight
- 12-lead ECG (10 min supine)
- C-SSRS Since Last Visit version
- MDS-UPDRS
- QUIP-RS
- Physical examination
- ESS
- PVT at 10:00 h, 12:00 h, 14:00 h and 16:00 h (\pm 0:15 h each) or individually adapted PVT schedule with the same timeframe as at VR. Upload data
- MoCA
- Collect and charge actigraphy device
- Read out actigraphy device, upload data
- Check subject diary (treatment diary)
- Collect subject diary (treatment phase diary, V3B only)
- PK blood sample

In case of early discontinuation, the same procedures as required for V3B will be performed.

6.1.6. Visits V1C and V2C

These end-of-washout visits are on-site visits and will take place

- on Day 21-1/+7 (V1C)
- on Day 42-1/+7 (V2C)

The washout periods can be extended from 1 week to 2 weeks, if this is more convenient for the subject.

The following procedures will be performed:

- Concomitant medication
- IMP dispensation
- Adverse event collection
- Vital signs (3 sets of orthostatic vital signs 15-20 min apart)
- 12-lead ECG (10 min supine)
- C-SSRS Since Last Visit version
- ESS
- PVT at 10:00 h, 12:00 h, 14:00 h and 16:00 h (\pm 0:15 h each) or individually adapted PVT schedule with the same timeframe as at VR. Upload data
- MoCA
- Issue actigraphy device (fully charged)
- Issue subject diary (treatment phase diary)
- Check subject diary (treatment phase diary)
- Collect subject diary (treatment phase diary)

- PK blood sample

6.1.7. Visit V3C

This follow-up visit is a phone call visit and will take place between Day 63 \pm 1 or 7 \pm 1 days after EDV (whatever comes first). This visit is also mandatory for subjects who discontinue early.

The following procedures will be performed:

- Concomitant medication
- Adverse event collection

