5.1.3. Timing of IMP doses and administration

IMP will be administered only to subjects included in this trial, following the procedures set out in the trial protocol.

IMP (2 capsules modafinil or placebo plus 2 capsules flecainide or placebo; 4 capsules in total) will be administered in the morning. IMP will be swallowed before meal with 150 mL tap water at 8:00 h (\pm 1 h).

For subjects aged above 65 years:

On the first, second and third day of each treatment period, 1 modafinil and 1 flecainide capsule will be taken. From the fourth to the last day of each treatment period, the regimen will be as described above.

The time of IMP intake will be recorded in the subject diary daily.

Dose adjustments will not be permitted.

In each treatment period, first IMP intake will take place on the day after IMP dispensation, i.e. on the day after visit VR, V1C or V2C, respectively.

In each treatment period, last IMP intake will take place on the day of visit V1B, V2B or V3B, respectively.

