Complete and accurate data on all AEs experienced, for the duration of the reporting period, will be reported on an ongoing basis in the AE pages of the eCRF.

The period of observation for the collection of AEs extends from the time when the subject gives informed consent until the date of final visit.

Serious adverse events occurring after a subject has taken the last dose of IMP will be collected until the date of final visit, regardless of the investigator's opinion of causation. Thereafter, SAEs are not required to be reported unless the investigator feels the events were related to either IMP administration or to a protocol procedure.

All AEs with onset or worsening after first intake of IMP until 7 days after last intake of IMP are defined as treatment emergent.

If a subject is documented as lost-to follow-up, ongoing/unknown outcome AEs will not be followed up.

For screening failure subjects, new AEs and updates must be recorded in the source and trial documents until the date the subject is determined to be a screening failure. Beyond this date, only SAEs will be followed up by CRO's pharmacovigilance representative.

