### 5.5.1 Adverse Events

AEs will be coded according to MedDRA Version 21.0.

Adverse event data includes:

- adverse event name
- start date
- stop date or ongoing
- severity (mild, moderate, severe)
- relationship to the IMP (unrelated, unlikely, possible, probable, definite)
- action taken with IMP (no action, drug interrupted, drug withdrawn, unknown)
- other actions (none, medication required, tests required, hospitalisation required or prolonged, other)

- outcome (recovered/resolved, recovered/resolved with sequelae, recovering/resolving, not recovered/not resolved, fatal, unknown) and date of outcome
- serious (yes or no)

All AEs will be presented in listings.

Adverse event summaries will focus on **treatment-emergent adverse events (TEAEs)**, defined as AEs with an onset or worsening after the first IMP intake and not more than 7 days after the last IMP intake.

If the start date of an AE is incomplete or missing, it will be assumed to be treatment-emergent except if the stop date or the incomplete start date indicates that the event started prior to the first IMP intake or later than 7 days after the last IMP intake.

Treatment-emergent adverse events will be assigned to treatments based on the treatment period containing the AE onset date. If the onset date of an adverse event is during a washout period, it will be assigned to the preceding treatment period. If the AE onset date is incomplete such that it could belong to more than one treatment period, the AE will be assigned to all treatments corresponding to such treatment periods.

Based on collected data the following will be determined and will be used in addition to AEs overall for presentation in the applicable tables and listings:

- **Serious Adverse Events (SAEs):** defined as AEs considered by the investigator as serious.
- **Related TEAEs:** defined as AEs with relationships to the IMP assessed as being “possible”, “probable” or “definite” and include AEs with missing IMP relationship assessments.
- **Unrelated TEAEs:** defined as AEs with relationships to the IMP assessed as being “unlikely” or “unrelated”.
- **Severe TEAEs:** defined as AEs assessed as being “severe” in intensity and include the events with missing severity assessment.
- **TEAEs leading to discontinuation:** defined AEs whose action taken with IMP is “drug withdrawn” or other action taken is “withdrawal from trial”.

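### The last adverse-event contact (V3C) may fall before the plan's own 7-day treatment-emergent window has ended, because its date is tied to Day 63 and allows an early tolerance

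*Protocol*

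**What the plan says.** **Analysis window.** Protocol 7.1.4 states: "All AEs with onset or worsening after first intake of IMP until 7 days after last intake of IMP are defined as treatment emergent". SAP 5.5.1 uses the same limit: "onset or worsening after the first IMP intake and not more than 7 days after the last IMP intake".

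**Collection window.** Under Protocol 7.1.4, observation for adverse events "extends from the time when the subject gives informed consent until the date of final visit". One exception follows: "Thereafter, SAEs are not required to be reported unless the investigator feels the events were related to either IMP administration or to a protocol procedure".

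**Last dose.** Protocol 5.1.3 says that in each period the "last IMP intake will take place on the day of visit V1B, V2B or V3B, respectively". Section 6.1.5 puts V3B on Day 56 ± 2.

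**Final visit.** Section 6.1.7 introduces V3C as follows: "This follow-up visit is a phone call visit and will take place between Day 63". The sentence goes on to give ± 1 day or, alternatively, 7 ± 1 days after EDV, with the earlier of the two prevailing. Section 4.4.2 repeats the 7 ± 1 days after EDV. The flow chart shows no contact after V3C.

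**Status of the day numbers.** Flow chart note 13 says that day numbers from Day 21 onward are only theoretical, because washouts are flexible. Protocol 3.1 describes a one-week follow-up after the last treatment period.

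**The concern.** The analysis counts events over 7 days after the last dose, while the schedule may stop collecting them sooner. An event starting between an early V3C and day 7 would belong in the treatment-emergent tables, but no scheduled contact would record it. The tables would then show unobserved days as event-free.

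This matters because safety is the primary objective (Protocol 2.1) and SAP 5.5.1 builds its adverse-event summaries on treatment-emergent events. The gap can arise only after treatment period III or after early discontinuation. After periods I and II, collection simply continues into the rest of the trial.

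**Working it through.** **Inputs.** Last dose on the V3B day (Protocol 5.1.3). V3B on Day 54 to 58 (6.1.5). V3C on Day 62 to 64, or 6 to 8 days after EDV (6.1.7, 4.4.2). Treatment-emergent limit of 7 days (7.1.4; SAP 5.5.1).

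**Formula.** Gap = V3C day − last-dose day. Shortfall = 7 − gap, when positive.

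**The plan's own figure.** Nominal gap = 63 − 56 = 7 days, which reproduces the one-week follow-up in Protocol 3.1. On nominal dates there is no shortfall.

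**Reading 1: V3C is 7 ± 1 days after V3B or EDV.** This takes note 13 and the one-week follow-up as the intention.
- After V3B: gap 6 to 8 days, so the shortfall is at most 7 − 6 = 1 day.
- After EDV with the last dose on that day: 6 to 8 days, again at most 1 day short.
- After EDV with the last dose one day or more earlier: at least 6 + 1 = 7 days, no shortfall.

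**Reading 2: both windows taken literally.** Five V3B days by three V3C days give 15 permitted pairs, with gaps from 62 − 58 = 4 to 64 − 54 = 10 days. Six pairs fall below 7:

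| V3B day | V3C day | Gap (days) | Shortfall (days) |
|---|---|---|---|
| 58 | 62 | 4 | 3 |
| 57 | 62 | 5 | 2 |
| 58 | 63 | 5 | 2 |
| 56 | 62 | 6 | 1 |
| 57 | 63 | 6 | 1 |
| 58 | 64 | 6 | 1 |

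With V3B on Day 58, every permitted V3C day is short. Under the earlier-date clause, an EDV on Day 57 allows V3C after 62 − 57 = 5 days, and one on Day 58 after 62 − 58 = 4 days.

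**Does Day 63 work as an anchor?** Each washout may be one week longer than nominal. With both extended, V3B moves to about 56 + 7 + 7 = Day 70, so Day 63 ± 1 comes before the last dose. With one extended, V3B is at about Day 63 itself. Literal Day 63 therefore cannot serve all subjects.

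**The proposed rule.** With V3C at 7 days −0/+2 after V3B or EDV, the gap after a V3B-day dose is 7 to 9 days. After EDV it is at least 7, because the last dose is on or before that visit.

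**The case against.** The strongest reply is that Day 63 was never meant literally. Note 13 and the one-week follow-up both point to V3C as a visit relative to the end of treatment. This stands, and it limits the assured shortfall to one day. It does not remove it, because the ± 1 tolerance still permits day 6, and Section 6.1.7 gives completers no anchor other than Day 63.

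A second reply is that the 7-day rule is a ceiling for classifying events and does not promise that all 7 days will be observed. That is a fair reading of the definition, but a table built on the ceiling is hard to interpret if some subjects were not followed up to it.

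A third reply is pharmacological. Protocol Table 1 gives terminal half-lives of 15 h for modafinil and 13 h for flecainide, so 4 days (96 h) is already 96 / 15 = 6.4 modafinil half-lives. This makes late exposure-driven events less likely. The documents describe no withdrawal phase, so a reader should not infer that withdrawal events are understated.

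Three other inferences are tempting and unsupported:
- **That 6 of 15 pairs means 40% of subjects.** The pairs are calendar possibilities, not equally likely outcomes, and the nominal gap is exactly 7. Nor does period III making up a third of treatment periods mean that all of it is affected.
- **That the attributable window is always shorter when a treatment is given last.** A washout can also be as short as 4 days (V1B on Day 16, V1C on Day 20). Dosing restarts the next day, and SAP 5.5.1 assigns later onsets to the next period. The real difference is that those later events are still collected.
- **That the comparison between treatments is biased.** Each treatment is last in two of the six sequences. Early discontinuers could differ by treatment, but the documents do not show that they would.

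**Conclusion.** The mismatch holds. Nothing in the protocol prevents V3C from closing routine collection before the 7-day window ends. The size depends on the reading: one day at most if V3C follows V3B or EDV by 7 ± 1 days, and one to three days if the day windows are literal. After EDV the shortfall is normally at most one day, and then only if the last dose was taken on the EDV day; more arises only where Day 63 ± 1 comes first.

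The possible loss is confined to non-serious events and serious events not judged related to IMP or a protocol procedure, with onset late in the window after period III or early discontinuation. How many subjects or events this would involve cannot be derived from the documents. The result assumes that the last dose is taken on the V3B day, as Section 5.1.3 requires; an earlier last dose lengthens the gap. This is a cheap improvement to ascertainment for the primary objective and does not threaten the treatment comparison.

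**What to change.** Reconcile Protocol 4.4.2, 6.1.7 and the flow chart so that V3C is dated from the actual V3B or EDV and not from Day 63. Allow no early tolerance (for example 7 days, −0/+2), and delete the clause that lets the earlier date prevail.

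The anchor should be the visit and not the last intake. SAP 4.6 and 5.6 provide for an EDV during washout, 6 or more days after the last intake, so a call timed from the last intake could fall on or before the EDV itself. Anchoring to V3B or EDV guarantees at least 7 days after the last dose in every case and keeps the follow-up after EDV that Section 4.4.2 requires.

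The cost is wording in three places and one phone call held up to a few days later for some subjects. No visit is added. If the visits have already taken place, the SAP could instead summarise the days from last intake to final adverse-event contact, so that a reader can see who was followed for fewer than 7.
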